Study Title: Improving Accessibility and Personalization of Cognitive Remediation for Schizophrenia

Clinicaltrials.gov: NCT03576976

Study Protocol

Date of Approval: 05/24/2018

Improving Accessibility and Personalization of Cognitive Remediation for Schizophrenia

Protocol Information:

IRB of Record: New York State Psychiatric Institute
Protocol # 7638

First Date of IRB Approval: 05/24/2018

Contact Principal Investigator: [name]

Co-Investigator(s): [name] [name]

NYSPI PI Division: Behavioral Health Services and Policy Research

Source of Funding: Federal

Institute/Agency: National Institute of Mental Health

Grant Name: Optimizing and Personalizing Interventions for Schizophrenia Across the Lifespan

Grant Number: 1 P50 MH 115843

Background, Significance and Rationale: Schizophrenia is associated with persistent neurocognitive deficits that do not respond to pharmacologic treatment and add to illness burden by imposing significant limitations on the ability to adhere to pharmacotherapy, benefit from psychosocial programs, and function in the social, vocational, and educational venues integral to community integration. Neurocognition is a crucial intervention target. Cognitive remediation (CR) is an evidence-based practice to treat the pervasive and significant cognitive deficits that contribute to functional decline in schizophrenia. New York State Office of Mental Health (NYS OMH) is the first and largest state system of care to implement a statewide program of cognitive remediation (CR), an evidence-based practice for improving cognition and aiding functional recovery. Through Cognitive Remediation to Promote Recovery (CR2PR), CR is offered in outpatient programs, with plans to expand to more services and further adapt implementation to improve treatment outcomes. This project will work directly with NYS OMH clinics that offer CR2PR to build upon and improve current methods of delivering cognitive remediation.

Purpose: This project studies the impact of two adaptations. One adaptation focuses on increasing the accessibility of the program, which participants report is limited by the requirement of twice-weekly attendance. This project will compare the delivery of CR in either two clinic-based sessions (Clinic) or one clinic and one remote session (Hybrid) per week. The second adaptation is intended to improve personalization of CR by systematically accounting for individual differences in neurocognitive needs. Drawing upon convergent evidence for tailoring CR based on need for early auditory processing (EAP) training, this project integrates a measure of EAP into the baseline assessment to facilitate personalization of the menu of restorative computer-based exercises used in CR. The primary purpose of data analyses is to inform the feasibility and acceptability of the adaptations. The primary outcome will be treatment satisfaction. The secondary outcomes will be change in neurocognition from pre- to post-treatment.

Study Locations: New York State Psychiatric Institute and NYS OMH Facilities:

- ✓ Washington Heights Community Service
- ✓ Creedmoor Psychiatric Center
- ✓ Kingsboro Psychiatric Center
- ✓ Manhattan Psychiatric Center
- ✓ Rockland Psychiatric Center
- ✓ South Beach Psychiatric Center

Description of Subject Population: The study sample includes adults with schizophrenia or schizoaffective disorder who are referred to and eligible for CR2PR.

Procedures: There are two phases of this study.

Phase 1: Staff training and Start up (Months 1-3).

The focus in this initial phase is staff training, using the same combination of web, telephonic and in person training currently in place for CR2PR. Clinic staff trained on cognitive assessment will be provided with and trained to administer the Tone Matching Test as an additional component of the baseline assessment administered for routine CR treatment planning. The CR2PR clinicians will be trained on hybrid delivery methods and to use the Tone Matching Test results to personalize the menu of cognitive exercises such that the treatment plan for only those identified as EAP impaired will include the EAP exercises that are available in the web-based programs used by CR2PR clinics. CR2PR clinicians will be trained on the protocol for Hybrid CR delivery.

Phase 2: Pilot Feasibility Trial (Months 4-36).

The focus of this phase is to implement and evaluate cognitive remediation.

Recruitment Methods: Participants will be recruited from New York State Office of Mental Health (OMH) psychiatric facilities where cognitive remediation (CR) is currently a clinical service (Cognitive Remediation to Promote Recovery, i.e. CR2PR) under the supervision of PI [name]. Research referrals will be tied to the current system of referrals for participation in each clinic's CR program. Clinical staff will refer potential participants to the CR clinician who will explain the program and invite participation. If clients are interested in CR services, the CR2PR clinician will send all referrals to a research assistant who will explain research procedures, obtain informed consent, and screen for eligibility. Patients who want CR but who do not want to participate in the study will continue with the standard CR service procedures. The research study will not be advertised.

Informed Consent: All clients who agree to an initial meeting with research assistant will have the full study explained to them, and will have ample opportunity to ask questions prior to signing consent. The process of informed consent will include explanation of the amount of time required, the possible risks/benefits of study participation, their right to refuse participation in the study without prejudice and alternatives to study participation, their right to terminate participation at any moment without prejudice, procedures to protect confidentiality, potential for de-identified data sharing, and the contact information for the PI and IRB.

Eligibility:

Inclusion Criteria	Methods of Ascertainment
1. Attending OMH Clinic	Referral by clinic personnel to the clinic's CR2PR program
2. Diagnosis of Schizophrenia or Schizoaffective disorder	Medical chart review and/or report from referring clinician and treating psychiatrist
3. Age 18-65	Client report, collected by research assistant
4. Full Scale IQ 70 or above	Wechsler Test of Adult Reading, administered by research assistant
5. English fluency	Wechsler Test of Adult Reading and observation during consent

5. Psychiatric and Behavioral stability

Columbia-Suicide Severity Rating Scale administered by research assistant and clinical team observation

Exclusion Criteria

Methods of Ascertainment

1. Unremitted substance dependence / dependence in the past 6 months

Medical chart review and/or report from referring clinician and treating psychiatrist

2. Neurological illness

Client report; Medical chart review

3. Traumatic brain injury in the last 2 years

Client report; Medical chart review

Procedures: A trained research assistant will obtain informed consent, screen for eligibility and obtain additional sociodemographic information. Participants will complete the standard CR2PR neurocognitive assessment battery plus the TMT with a trained clinician. Following completion of the baseline assessment, participants will be randomized using a pre-determined randomization sequence made by the research team to either Clinic or Hybrid CR.

Clinic CR: This is the evidence-based CR intervention currently in use at the OMH clinics. The Clinic research arm consists of 30 sessions delivered at 2 times per week in a group format of up to 8 participants with rolling admission. Each session consists of 45 minutes of working on 3-4 computerized exercises to improve specific cognitive skills. CR2PR clinicians are trained to select cognitive exercises from a menu of web-based programs to improve the cognitive functions identified as impaired on the assessment, e.g., attention, memory. With the addition of the TMT, they will be able to identify EAP as a focus area. Computer exercises are followed by 15-minute manualized discussion groups which promote generalization of cognitive gains on computer activities to functional gain by encouraging participants to link within-session cognitive activities to daily activities and recovery goals.

Hybrid CR: The Hybrid condition consists of 15 clinic sessions in the above format, and independent work on cognitive exercises for 60 minutes per week for 15 weeks using a laptop, PC or tablet available to them (at home, school, clinic, library). Independent work on designated web-based computer exercises can be done in multiple or in one sitting. Clients will keep logs of their activities and issues related to remote practice. During the in-clinic session, the clinician will review their remote activities, problem-solve any access or activity related issues, provide personalized bridging, encouragement and feedback, and review the exercises to be completed remotely before the next clinic-based session. Clinicians will also maintain logs of their experiences with remote sessions to document issues pertinent to feasibility and effectiveness.

Throughout treatment in both conditions, CR clinicians document service utilization by tracking scheduled sessions, attendance, treatment dropout and completion. PI [name] will continue to provide supervision of CR clinicians as a part of overseeing the CR2PR program.

Within one week following treatment completion, clients will be assessed for treatment satisfaction and change in neurocognitive functioning by a research assistant. Treatment completion is defined as at least 20 of 30 clinic sessions for the Clinic condition and at least 10 of 15 clinic sessions for the Hybrid condition. A research assistant will conduct a semi-structured debriefing interview with each participant in the Hybrid condition about their experience using remote technology. At Study months 15 and 30, a research assistant will conduct a semi-structured debriefing interview with each CR2PR clinician about remote technology use and how the tone matching test informed the choice of cognitive exercises.

Criteria for Early Discontinuation: Criteria for early discontinuation from the study will follow clinic-based guidelines. A person is discontinued from a service if they are no longer able to attend due to scheduling conflicts (e.g., work/school), hospitalization for medical or substance use treatment, inpatient psychiatric hospitalization, or discharged from the clinic. The CR2PR clinician will use clinical judgment as to the appropriateness of continued participation for each participant, taking into account evidence of clinical worsening, suicidality, or other issues that may arise during participation. Consultation with the PI will be sought through routine supervision prior to discontinuation. No additional criteria will be used for research purposes.

Assessment Measures: Screening measures include the Wechsler Test of Adult Reading (WTAR-5) and Columbia Suicide Severity Rating Scale. The Tone Matching Test is included in the assessment battery to tailor the CR treatment plan. The primary outcome measure will be treatment satisfaction. The secondary outcome will be change in neurocognition from baseline to post-treatment (approximately 15 weeks).

- **The Wechsler Test of Adult Reading (WTAR-5)** will be used to estimate premorbid intellectual functioning and determine eligibility (Full Scale IQ \geq 70). This assessment takes 3-5 minutes.
- **The Columbia-Suicide Severity Rating Scale** will be used to assess psychiatric stability. Should suicidal ideation or behavior be endorsed, imminent risk will be further evaluated by the assessor and appropriate, immediate action will be taken. This assessment takes 5-10 minutes.
- **The Tone Matching Test (TMT)** consists of pairs of 100-ms tones that are either the same or differ in pitch between 2.5 and 50%, with a 500-ms inter-tone interval. The participant listens to each tone pair and indicates whether the tones were the same or different. A cut-off score of 70% correct classifies EAP as impaired or intact. This test takes approximately 7-10 minutes and will be administered by the designated clinician at each clinic at baseline.
- **Treatment Satisfaction:** Following completion of CR, all clients are asked to complete a questionnaire rating satisfaction with the treatment experience, working alliance with the CR clinician, and perceived benefits from the intervention. Items are rated on a scale of 1 to 6. The outcome measure is an average of all ratings with higher ratings indicating greater satisfaction. This measure takes approximately 2 minutes to complete. Treatment satisfaction will be compared between groups.
- **Neurocognition:** The Brief Assessment of Cognition in Schizophrenia (BACS) is a standardized battery. Selected subtests will assess verbal memory, working memory, speed of processing, and executive function. The tests will take approximately 25 minutes to complete. It is routinely administered by a designated CR2PR clinician at each clinic before treatment. A trained research assistant will administer the battery at post-treatment. The Continuous Performance Test – Identical Pairs (CPT-IP) is a computerized test that assesses attention/vigilance. Participants view numbers flashed on a computer screen and are to respond when the same number appears twice in a row. The test takes 14 minutes to complete. It is routinely administered by the designated CR2PR clinician at each clinic before treatment. A trained research assistant will administer the test at post-treatment. The outcome measure is an average T score from all neurocognitive subtest T scores. Change in neurocognition will be compared between groups.

Research Related Delay to Treatment: Research procedures will not result in a delay to treatment. All clients will have access to the Cognitive Remediation program provided routinely at their clinic.

Clinical Treatment Alternatives: All clients who decline to participate in research will continue the usual process of intake into their clinic's CR program. They may receive cognitive remediation as usual.

Risks/Discomforts/Inconveniences: The main risk is loss of confidentiality. In addition, patients may become mildly uncomfortable or tired during assessments or during cognitive training. However, no adverse reactions to the assessments or interventions have been reported during the two years the clinical service has been in place at the clinics or in preliminary studies. The software used in this study is the same or similar to that used in clinical practice in New York state OMH clinics with high levels of satisfaction. Although there are no anticipated risks as a function of the assessments or intervention, given that the sample involves people with psychotic disorders, it is conceivable that participants may feel burdened by procedures, or may experience psychiatric symptom exacerbation unrelated to the study.

Methods to Minimize Risk:

Confidentiality: The primary risk is loss of confidentiality. Procedures associated with potential loss of confidentiality, and measures to protect confidentiality are listed in the consent form. A HIPAA Authorization form, reviewed at the time of informed consent, lists those entities with whom knowledge of participation and data may be shared. Confidentiality will be preserved by coding all hard copy data sheets, session logs, and electronic files using a unique numerical identifier not linked to personal identifying information (e.g. name, date of birth). Consent forms will contain identifying information but will not be coupled with numerical identification numbers. Study computers used for collecting and storing data will be encrypted. Hard copy data will be maintained in a locked file cabinet and electronic files will be stored on password protected, encrypted computers, in a locked office at NYSPI. Only the research team will have access to electronic data. Public dissemination of the results of this research will contain no identifying information about individual subjects. Data deposited into appropriate repositories for public sharing will be stripped of any personal identifying information to protect confidentiality.

Burden or Fatigue: During assessments, breaks and refreshments may be provided to minimize burden or fatigue and, if feasible, assessment sessions may be divided. OMH clinicians have been trained to attend to signs of burden or fatigue during assessments and intervention. Participants will discuss their treatment experience with the CR clinician on a weekly basis. This will assist clinicians in trouble-shooting challenges (clinical or practical) to participation and minimize perceived burden. In-clinic, breaks during treatment sessions are and will continue to be offered as needed. Patients completing remote sessions may self-pace their completion of exercises and may do them in a location that is convenient and comfortable.

Unanticipated Adverse Events: A trained research assistant will administer the Columbia-Suicide Severity Rating Scale during the screening appointment to assess psychiatric stability. Should suicidal ideation or behavior be endorsed, imminent risk will be further evaluated by the assessor and appropriate, immediate action will be taken, similar to what is outlined for clinical worsening. PI [name] will coordinate with CI [name] to ensure that all research personnel are trained in safety procedures. Supervision of cognitive remediation clinicians with PI [name] includes monitoring of patients' clinical stability and ability to continue with treatment sessions. Clinical worsening will be reported to PI [name] by research and clinical personnel and will be

handled as per clinic safety procedures. Clinical worsening is defined as an increase in symptoms (e.g., hallucinations, paranoia) that causes significant distress, poses imminent risk, and/or impairs the ability of the individual to participate in study procedures. The consent form states that if the participant experiences an increase in symptoms or distress, the study personnel should be informed and will assist the participant in getting the help they need. When research personnel encounter clinical worsening during any study-related procedure they will 1) assist the subject in contacting their primary case worker, therapist, or psychiatrist and 2) report the urgent clinical issue to PI [name]. In the unlikely situation that a subject is deemed to be an imminent risk to self or others (i.e., expresses imminent suicidal or homicidal ideation), the study personnel will physically walk the subject to their primary case worker, therapist, or psychiatrist. Further course of action may include contacting security to escort the participant to the emergency room or to call 911. Any unanticipated adverse event will be reported immediately to PI [name] by the cognitive remediation clinician or research personnel.

Certificate of Confidentiality: This study will be conducted under a Certificate of Confidentiality.

Direct Benefits to Subjects: Cognitive remediation and computerized learning software have been used in many psychiatric patient populations in various settings and are well-recognized procedures without serious risk. There is potential for direct benefit to the patient participants, such as improvement in cognition, and potential benefits for the treatment of other people with neuropsychiatric disorder.

Compensation or Reimbursement: Participants will be compensated \$40 for the baseline assessment and \$60 for the post-treatment assessment.

References

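### Does the plan need an analysis of Tone Matching Test personalization, given that only delivery format is randomised?

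*Protocol*

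**What the plan says.** The Protocol's Purpose section states "This project studies the impact of two adaptations". The first is delivery of cognitive remediation in two clinic sessions a week, or in one clinic and one remote session. For the second, the text says that "this project integrates a measure of EAP into the baseline assessment to facilitate personalization", where EAP is early auditory processing. The section then gives the aim of the analyses: "The primary purpose of data analyses is to inform the feasibility and acceptability of the adaptations".

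The tailoring rule is under Procedures, Phase 1: "the treatment plan for only those identified as EAP impaired will include the EAP exercises". Assessment Measures fixes the impaired/intact cut-off at 70% correct.

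On sequence, the Procedures text after Eligibility says "Participants will complete the standard CR2PR neurocognitive assessment battery plus the TMT with a trained clinician", and that after this baseline assessment "participants will be randomized using a pre-determined randomization sequence made by the research team to either Clinic or Hybrid CR". TMT use is described under Clinic CR. For the other arm, "The Hybrid condition consists of 15 clinic sessions in the above format".

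The same Procedures text plans interviews with each clinician at study months 15 and 30, covering remote technology and how the TMT guided exercise choice. Client interviews are confined to the Hybrid arm and to remote technology.

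The available SAP text names two outcomes, satisfaction (primary) and change in average neurocognitive T score (secondary). It compares Clinic with Hybrid on each by Wilcoxon's rank sum test and does not mention the TMT.

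**The concern.** The Protocol names two adaptations and says it studies the impact of both, and personalization is in the study title. A statistician would then look for a contrast that isolates each one. There is a randomised contrast for delivery format and none for personalization. Nor does the available SAP text plan any figure specific to personalization, such as how many clients were classed as impaired or how often the exercise rule was followed.

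Two things would be at stake. A reader could expect an effect estimate for personalization that the design cannot give, or could take a favourable overall result as support for it. And even on the modest reading, feasibility and acceptability, one of the two adaptations would have no planned quantitative result.

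**Working it through.** The documents state no sample size, power, effect size or standard deviation, so there is no planned figure to reproduce. The check sets the design against the stated aim.

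**Step 1. Levels of each adaptation by arm** (Protocol, Purpose and both Procedures sections)

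| Adaptation | Clinic arm | Hybrid arm | Varies between arms? |
|---|---|---|---|
| Delivery format | clinic only | clinic plus remote | yes, randomised |
| TMT-guided exercise menu | present | present | no |

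Personalization is present in 2 of 2 arms. Of the 2 comparisons in the available SAP text, 0 use TMT status.

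**Step 2. What the randomised contrast estimates.** Write Y(f, p) for the outcome under format f (H for Hybrid, C for Clinic) and personalization p (1 present, 0 absent). The trial compares outcomes under Y(H, 1) and Y(C, 1). An effect of personalization would compare Y(f, 1) with Y(f, 0), and no participant is treated under p = 0. The first part of the concern is therefore correct.

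**Step 3. Whether TMT status could stand in for the missing arm.** Under the Phase 1 rule, auditory exercises go to impaired clients only. If the rule is followed, an indicator for receiving the exercises equals the indicator for baseline impairment. An impaired-versus-intact comparison then mixes baseline auditory impairment with exercise content and cannot separate them. Post-treatment data have a further limit: "Within one week following treatment completion, clients will be assessed for treatment satisfaction and change in neurocognitive functioning by a research assistant". Satisfaction or T-score change by TMT status would thus describe treatment completers only. Such rows would say nothing about whether personalization works, so planning them brings no gain.

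**Step 4. Whether the randomised comparisons are harmed.** The TMT precedes allocation, so TMT status is a baseline characteristic that randomisation balances in expectation. A feature common to both arms cannot bias the difference between them. The comparison estimates the effect of format within TMT-guided remediation. Both planned tests stand as written.

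**Step 5. What the stated aim requires.** The Purpose section uses the language of comparison for format alone. For the TMT it speaks of adding a baseline measure to assist tailoring, and it rests the tailoring on existing evidence. Phase 2 is labelled a pilot feasibility trial. No hypothesis about, or outcome for, an effect of personalization is stated.

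**Step 6. What will be available on personalization.**
- *Share classed as impaired:* a baseline TMT result for every participant and a fixed 70% cut-off. It can be counted with no new data.
- *How clinicians used the result:* interviews at 2 time points, months 15 and 30. Of the 2 interview streams, 1 covers the TMT.
- *Acceptability of the personalized package as a whole:* satisfaction, attendance, dropout and completion, all planned. None isolates the TMT component.
- *Adherence to the exercise rule:* not among the items clinicians are said to track. Treatment plans may show it. Hybrid client logs and the clinician's weekly review of remote work may show part of it, for that arm only.

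**The case for a change.** The strongest case for a change is that it would cost very little. The stated purpose speaks of adaptations in the plural, so the feasibility of personalization is itself something the analyses are meant to inform. Yet the available SAP text does not commit to reporting the share impaired or adherence to the exercise rule, and no method is given for summarising the clinician interviews. One sentence in the Purpose section and a short descriptive table would close the gap with no new arm, patients or test.

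Part of this stands. *Impact* is too strong for the second adaptation, and a report that gave the share impaired, adherence where it can be retrieved and a summary of the clinician interviews would be better than one that did not. Three things keep it from becoming a required change. First, the share impaired is an ordinary baseline descriptor, and a SAP that says its analyses will focus on one comparison does not exclude describing the sample. Second, for a component delivered through clinicians' choice of exercises, interviewing those clinicians is a legitimate way to study feasibility. Third, the claim that nothing is planned rests on incomplete text, since part of the SAP was not available.

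**Conclusion.** The design observation is correct, but it does not call for a change to the plan. No planned or described comparison can estimate an effect of TMT-guided personalization: it is present in 2 of 2 arms, and its exercise content follows baseline status. The Protocol does not commit itself to such an estimate. Read whole, the Purpose section randomises and compares delivery format, adds the TMT as a common assessment step, and asks about feasibility and acceptability. Randomising one factor with a shared component in both arms is a fair design choice for a pilot.

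The effect on the two planned comparisons is nil. The residue is one overstated word and descriptive detail that analysts would fill sensibly, chiefly the number and share classed as impaired at the 70% cut-off. Breaking outcomes down by TMT status would add nothing on personalization and could invite a causal reading.

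This rests on two conditions: that the Phase 1 exercise rule is applied in both arms, as the text implies, and that the trial report claims no effect of personalization. The statement about the SAP is limited to the text that was available.

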## **Improving Accessibility and Personalization of Cognitive Remediation for Schizophrenia**

Statistical analyses for this project will focus on the comparison of proximal outcomes between Clinic and Hybrid delivery methods of Cognitive Remediation. There are two proximal outcomes: Treatment Satisfaction (primary) and Neurocognition (secondary).

Wilcoxon's rank sum test will be used to compare Clinic and Hybrid CR groups on treatment satisfaction at post-treatment and change on the average neurocognitive T score from baseline to post-treatment.

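### Tone Matching Test class is known before randomization and sets part of the treatment content, but no stratification by it is described and the SAP comparison makes no use of it

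*Protocol*

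**What the plan says.** **Timing.** Protocol, Procedures (after Eligibility): "Participants will complete the standard CR2PR neurocognitive assessment battery plus the TMT with a trained clinician". Then: "Following completion of the baseline assessment, participants will be randomized using a pre-determined randomization sequence made by the research team", to Clinic or Hybrid cognitive remediation. This is the only description of the sequence. It does not say whether allocation is simple, blocked or stratified, by TMT class or by site.

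**Classification.** Protocol, Assessment Measures, Tone Matching Test: "A cut-off score of 70% correct classifies EAP as impaired or intact".

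**Consequence for content.** Protocol, Procedures, Phase 1: "the treatment plan for only those identified as EAP impaired will include the EAP exercises". For the Clinic arm, the protocol says of the clinicians: "With the addition of the TMT, they will be able to identify EAP as a focus area". For the other arm: "The Hybrid condition consists of 15 clinic sessions in the above format". The same tailoring rule therefore applies in both.

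**Analysis.** SAP: "Wilcoxon's rank sum test will be used to compare Clinic and Hybrid CR groups on treatment satisfaction at post-treatment", and the same test for change in the average neurocognitive T score. The SAP text available mentions no stratum, covariate or breakdown by TMT class.

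**Aim.** Protocol, Purpose: the project has two adaptations, delivery and personalization, and the analyses are mainly to inform the feasibility and acceptability of both.

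**The concern.** The TMT class is a two-level baseline factor that the trial itself introduces. It is on file at allocation and decides whether auditory exercises are in a participant's plan. Clinic sessions hold 3-4 exercises in 45 minutes, so EAP exercises take time that an intact participant spends on something else.

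Three things are at stake:

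- **Chance imbalance.** If the sequence is unstratified and the sample small, one arm can by chance hold more EAP-impaired participants. The arms then differ in exercise mix as well as delivery, and a plain two-group test has no means of allowing for it.
- **Precision.** If the classes differ in outcome, that variation stays in the error term.
- **The second adaptation.** Pooling the classes leaves no statistical summary that shows how either outcome looks in participants whose plan was changed by the TMT.

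**Working it through.** The documents available give no sample size, allocation ratio, EAP-impaired prevalence, standard deviation or effect size, so there is no planned figure to reproduce. Everything below is an illustration. Assumptions: 1:1 allocation, simple (unstratified) randomization, prevalence p of 30% or 50%, and a class effect e of 0.3, 0.5 or 0.8 residual SD on the outcome.

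**1. Chance of imbalance.** With n per arm, the impaired counts X1 and X2 are independent Binomial(n, p). The probability that |X1 − X2|/n is at least 0.20, computed exactly:

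| n per arm | p = 50% | p = 30% |
|---|---|---|
| 20 | 26.8% | 22.6% |
| 30 | 15.5% | 12.0% |
| 40 | 9.3% | 6.7% |
| 50 | 5.7% | 3.8% |
| 60 | 3.5% | 2.2% |

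**2. Effect of a 20-point imbalance on the contrast.** Shift = 0.20 × e, which is 0.06, 0.10 and 0.16 SD for e = 0.3, 0.5 and 0.8.

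**3. Variance due to class at p = 50%.** Share = 0.25e²/(1 + 0.25e²):
- e = 0.3: 0.0225/1.0225 = 2.2%
- e = 0.5: 0.0625/1.0625 = 5.9%
- e = 0.8: 0.16/1.16 = 13.8%

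**4. Type I error of the plain rank sum test** (40,000 simulated trials per scenario, p = 50%, 20 to 60 per arm, two-sided 0.05). Overall it is 0.048 to 0.052 in every scenario. Among only those trials with an imbalance of 20 points or more it is:
- e = 0.3: 0.053 to 0.060
- e = 0.5: 0.061 to 0.083
- e = 0.8: 0.076 to 0.133

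**5. Power** (normal approximation, 30 per arm, p = 50%, arm effect 0.5 residual SD). Ignoring class, the SD is √(1 + 0.25e²); with the class variance removed it is 1, and power is 0.491.
- e = 0.3: 0.482 to 0.491, gain 0.9 points
- e = 0.5: 0.468 to 0.491, gain 2.3 points
- e = 0.8: 0.436 to 0.491, gain 5.5 points

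This approximation charges nothing for stratifying. Simulating van Elteren's test against the plain rank sum test includes that price. It shows a loss of about 1 point or less if the class has no effect, a change of under 1 point at e = 0.3, a gain of about 0 to 2 points at e = 0.5, and a gain of about 3 to 7 points at e = 0.8.

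**The case against.** **The protocol is silent; it does not rule stratification out.** A reader might infer that the sequence ignores TMT class. The documents do not support that: they say only that the sequence is fixed in advance and made by the research team. This stands. The table in step 1 applies only if allocation is in fact unstratified. The gap in the analysis does not depend on how the sequence was built.

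**Class may not be prognostic.** A reader might also infer from the Purpose section that TMT class predicts outcome. That section cites evidence for tailoring by need, meaning that impaired participants benefit from EAP exercises. It does not say that the classes differ in outcome once each has its tailored plan, and nothing in the documents suggests they differ in satisfaction, the primary outcome. This stands. The 0.3 to 0.8 SD range is assumed.

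**EAP is one of several tailoring factors.** Clinicians choose exercises for whatever functions test as impaired, in both arms. Individual content is part of the intervention, and a different mix of profiles is ordinary covariate imbalance. That largely stands, and it rules out calling this confounding. TMT class still differs in being a single binary rule that the trial adds and names as an adaptation under study.

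**The interviews already cover personalization.** The protocol plans debriefing of Hybrid participants about remote technology, and of clinicians about remote use and how the TMT informed exercise choice. This covers part of the question qualitatively. It gives no outcome data by class.

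**Small gain in a pilot.** True: a few power points at best, and near zero if the class effect is small.

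**Conclusion.** The point holds as a modest one. The class is known before allocation and determines part of the content in both arms. No stratification by it is described, and the SAP comparison available makes no use of it. A reader might take this as a biased comparison, but it is not one: the tailoring rule is common to both arms, randomization balances the class in expectation, and overall type I error holds.

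The cost is threefold. Some precision is lost if the class is prognostic. If the sequence is unstratified, a small sample is exposed to an imbalance that makes the result harder to interpret. And no statistical analysis bears on the personalization adaptation. The first two depend on assumed sample size, prevalence and class effect, so their size cannot be fixed from the documents. The third does not depend on those assumptions, though part of the SAP was not available for review.

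**What to change.** **In the SAP, for both outcomes:**

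- Prespecify a comparison stratified by TMT class (van Elteren's rank sum test), or one adjusted for class. Fix this before outcomes are seen, because adjustment added after an imbalance is noticed is open to challenge.
- Report the EAP-impaired share by arm.
- Tabulate satisfaction and neurocognitive change by arm within TMT class, labelled descriptive only. This table would not estimate the effect of personalization, since the tailoring rule is the same in both arms.

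**In the protocol:** state whether the sequence is stratified, and by what. Stratify it by TMT class only if enrolment has not begun and the strata would not become too thin alongside site, given the six OMH facilities listed. If they would, handle one of the two factors by adjustment. If enrolment has begun, the analysis change alone is enough.

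**Cost:** a few lines in the SAP and no new data. The downside is a loss of about 1 power point or less if the class is unrelated to outcome. Stratified allocation would also require the TMT to be scored before randomization.
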